## 1. Administrative Information

Trial registration number: ISRCTN registry - ISRCTN04386758

This SAP is based on protocol version 1.0 (date 02/11/2016)

#### **SAP** revision history

| Protocol
version | Updated SAP version no. | Section number changed                        | List of changes
from previous
version/protocol | Author of change | Date       |
|---------------------|-------------------------|---|--|------------------|------------|
| V1.0                | V1.0                    | n/a   | No changes from analysis planned in the protocol     | n/a              | 25/09/2017 |
| V1.0                | V2.0                    | Section 5, Appendix 2, Appendix 3, Appendix 5 | See below  | [name] | 27/02/2019 |

#### Changes from SAP v1.0

- We added a secondary analysis which estimates the effect of the intervention amongst patients who undergo surgery during the follow-up period. This secondary analysis applies to the primary outcome, and to acute cardiac events at 24 hours and 30 days. This analysis is described in section 5. Stata code to implement this analysis has been added to Appendix 3. A table (table 7) for reporting the results of this analysis has been added to appendix 5.
- We added a new appendix (appendix 2) which details how protocol deviations will be derived from the source data.
- We modified table 16 in appendix 5 to include separate lines for "incorrect dose of inotrope" and "inotrope not given". In v1.0 these were reported combined in one line.
- We added table 17 to appendix 5 which reports reasons for protocol deviations.

#### Timing of SAP revisions in relation to unblinding of data/results

- Version 1.0 of the SAP was written whilst all contributors had no access to unblinded trial data or to trial results.
- Version 2.0 of the SAP was written after GF had access to blinded trial data (i.e. a trial dataset with variable for treatment allocation removed, and any variables that reveal treatment allocation removed). No other contributors had access to the trial dataset or to trial results.

#### **Remit of SAP**

The purpose of this document is to provide details of the statistical analyses and presentation of results to be reported within the principal paper(s) of the OPTIMISE II trial. Subsequent papers of a more exploratory nature (including those involving baseline data only) will not be bound by this strategy but will be expected to follow the broad principles laid down in it. Any exploratory, post hoc or unplanned analyses will be clearly identified in the respective study analysis report.

# 2. Background and trial design

| Study objectives        | Primary Objective To establish whether the use of minimally invasive cardiac output monitoring to guide protocolised administration of intra-venous fluid, combined with low dose inotrope infusion for patients undergoing major elective surgery involving the gastro-intestinal tract will reduce the incidence of postoperative infection within 30 days of randomisation.  Secondary Objectives To determine whether cardiac output-guided haemodynamic therapy reduces mortality, other forms of postoperative morbidity, improves quality of life and is cost-effective.                        |
|-------------------------|--|
| Study design            | International, open, multi-centre, two arm, parallel group, randomised controlled trial  |
| Setting                 | Surgical services of hospitals undertaking major elective surgery involving the gastrointestinal tract in participating countries.   |
| Participants            | 
 
Inclusion Criteria
 
Patients aged 65 years and over undergoing major elective surgery involving the gastrointestinal tract that is expected to take longer than 90 minutes.
 
  |
|                         | 
 
Exclusion Criteria
 
Patient refusal
 
Clinician refusal
 
American Society of Anesthesiologists (ASA) score of I
 
Patients expected to die within 30 days
 
Acute myocardial ischaemia in previous 30 days
 
Acute pulmonary oedema in previous 30 days
 
Any contra-indication to low-dose inotropic medication
 
Pregnancy
 
Previous enrolment in the OPTIMISE II trial
 
Current participation in another clinical trial of a treatment with a similar biological mechanism or primary outcome measure
 
 |
| Interventions           | Intervention Group A cardiac output—guided hemodynamic therapy algorithm for intravenous fluid and inotrope (dopexamine or dobutamine) infusion during and for four hours following surgery  Usual Care Group Patients in the control group will be managed by clinical staff  |
| Primary outcome measure | according to usual practice.  Postoperative infection within 30 days of randomisation. This is defined as one or more of the following infections of Clavien-Dindo grade II or greater:  |

- i. Superficial surgical site infection;
- ii. Deep surgical site infection;
- iii. Organ space surgical site infection;
- iv. Pneumonia;
- v. Urinary tract infection;
- vi. Laboratory confirmed blood stream infection;
- vii. Infection, source uncertain; this is defined as an infection which could be more than one of the above (i.e. i-vi), but it is unclear which.

#### 3. Outcome measures

#### Primary outcome measure

The primary outcome is postoperative infection within 30 days of randomisation. This is defined as one or more of the following infections of Clavien-Dindo grade II or greater, more detail on the definition of each type of infection is available in the OPTIMISE II protocol:

- i. Superficial surgical site infection;
- ii. Deep surgical site infection;
- iii. Organ space surgical site infection;
- iv. Pneumonia;
- v. Urinary tract infection;
- vi. Laboratory confirmed blood stream infection;
- vii. Infection, source uncertain; this is defined as an infection which could be more than one of the above (i.e. i-vi), but it is unclear which.

The process for determining whether the primary outcome has been observed or not is described as missing is given in Appendix 0.

#### Secondary outcomes

- Mortality within 180 days of randomisation
- Acute kidney injury of Clavien-Dindo grade II or greater, within 30 days of randomisation
- Acute cardiac event of Clavien-Dindo grade II or greater, within 24 hours of randomisation (safety outcome)
- Acute cardiac event of Clavien-Dindo grade II or greater, within 30 days of randomisation (safety outcome)

Full definitions of secondary outcome measures can be found in the OPTIMISE II protocol.

#### **Process Measures**

- Duration of hospital stay (number of days from randomisation until hospital discharge)
- Number of critical care free days up to 30 days from randomisation (a critical care free day is defined as a day in which the patient is alive and is not in a level 2 or level 3 critical care bed)

# 4. Sample size and randomisation

#### Sample size calculation

In order to detect a 5% absolute reduction (from 30% to 25%) for the primary outcome of postoperative infection up to 30 days (a risk ratio of 0.83), with 80% power, and an overall type I error rate of 5%, we require 2502 patients (1251 per arm). This sample size would also allow us to detect an absolute reduction in the primary outcome of 6% (from 30% to 24%) with 92% power.

[figure not shown]
#### **Randomisation procedure**

Randomisation will occur after the patient has provided informed consent and shortly before the surgical procedure is due to start. Patients will be centrally allocated to treatment groups in a 1:1 ratio by minimisation with a random component. Minimisation variables will be country, surgical procedure category, and American Society of Anesthesiologists (ASA) grade. The surgical procedure categories are: i) resection of colon, rectum or small bowel; ii) resection of pancreas and bowel; iii) resection of stomach (non-obesity surgery); iv) resection of oesophagus (non-obesity surgery); v) obesity surgery; vi) other surgery involving gut resection. The ASA grades are: II, III, and IV. Each patient will be allocated with 80% probability to the group that minimises the between group differences in these factors among all patients recruited to the trial to date, and to the alternative group with 20% probability. To enter a patient into the OPTIMISE II trial, research staff at the site will log on to a secure web-based randomisation and data entry platform hosted by Queen Mary University of London and complete the patient's details to obtain a unique patient identification number and allocation to a treatment group. A patient's treatment group allocation will only be revealed to the person performing randomisation.

# 5. Analysis methods

## Information for CONSORT flow diagram

The following information will be provided in the CONSORT flow diagram:

#### **Baseline characteristics**

Baseline characteristics will be summarised for each treatment group by the mean and standard deviation or median and interquartile range for continuous variables, and the number and percent for categorical variables. Draft tables are given in Appendix 5.

#### **General analysis principles**

Analyses will follow the intention-to-treat principle: all randomised patients with a recorded outcome will be included in the analysis, and analysed according to the treatment to which they were randomised (1). Definitions of what constitutes a recorded outcome for each outcome can be found in Appendix 1. Patients with missing outcome data will be excluded from the analysis. Missing data for baseline covariates to be included in the analysis model will be accounted for using mean imputation (2).

For the analysis of the primary outcome, each secondary outcome, and all process measures, we will present the following information:

- The number of patients included in each analysis, by treatment arm
- A summary statistic of the outcome (e.g. number (%)), by treatment arm
- The estimated treatment effect
- A 95% confidence interval for the estimated treatment effect
- A two-sided p-value

For all analyses, a significance level of 5% will be used.

#### **Analysis of primary outcome**

The primary outcome, postoperative infection within 30 days of randomisation, will be analysed using a mixed-effects logistic regression model with a random intercept for country (3), adjusting for planned surgical procedure, ASA grade, gender, age, baseline haemoglobin, and baseline creatinine. Planned surgical procedure and ASA grade will be included as the model as categorical variables. The categories for planned surgical procedure are i) resection of colon, rectum or small bowel; ii) resection of pancreas and bowel; iii) resection of stomach (non-obesity surgery); iv) resection of oesophagus (non-obesity surgery); v) obesity surgery; vi) other surgery involving gut resection. The categories for ASA grade are II, III, and IV. Age, baseline haemoglobin, and baseline creatinine will be modelled using using restricted cubic splines with three knots (with knot locations based on Harrell's recommendations: 10th percentile, 50th percentile and 90th percentile of covariate) (4, 5).

#### **Analysis of secondary outcomes**

#### Mortality within 180 days of randomisation

Mortality within 180 days will be analysed using a mixed-effects logistic regression model with a random intercept for country (3), adjusting for planned surgical procedure, ASA grade, gender, age, baseline haemoglobin, and baseline creatinine. Planned surgical procedure and ASA grade will be included in the model as categorical variables, and age, baseline haemoglobin, and baseline creatinine will be modelled using restricted cubic splines using the same approach as for the analysis of the primary outcome above (4, 5).

#### Acute cardiac event within 30 days of randomisation

This outcome will be analysed using the same model as 'mortality within 180 days of randomisation' above.

#### Acute kidney injury within 30 days of randomisation

Acute kidney injury within 30 days will be analysed using a mixed-effects logistic regression model with a random intercept for country (3), adjusting for planned surgical procedure, ASA grade, age, and baseline creatinine. Planned surgical procedure and ASA grade will be included in the model as categorical variables, and age and baseline creatinine will be modelled using restricted cubic splines using the same approach as for the analysis of the primary outcome above (4, 5).

The expected event rate for this outcome is lower than for other outcomes, and as such we have reduced the number of covariates included in the model to ensure a sufficient number of events per variable.

#### Acute cardiac event within 24 hours of randomisation

Acute cardiac event within 24 hours will be analysed using a logistic regression model, adjusting for ASA grade and age. ASA grade will be included in the model as categorical variables, and age will be modelled using restricted cubic splines using the same approach as for the analysis of the primary outcome above

The expected event rate for this outcome is lower than for other outcomes, and as such we have reduced the number of covariates included in the model to ensure a sufficient number of events per variable.

#### **Analysis of process measures**

#### Duration of hospital stay

Duration of hospital stay will be analysed using a competing-risk time-to-event model (6), which includes mortality as a competing risk for hospital discharge. The model will include adjustment for planned surgical procedure, ASA grade, gender, age, baseline haemoglobin, and baseline creatinine. Planned surgical procedure and ASA grade will be included in the model as categorical variables, and age, and baseline creatinine will be modelled using restricted cubic splines using the same approach as for the analysis of the primary outcome above (4, 5). Because there are no facilities for analysing competing risk data using mixed-effects models in Stata, we will use robust standard errors which account for clustering by country.

For each treatment arm we will present median and interquartile range for length of hospital stay for patients who survived to hospital discharge. We will also present for each treatment arm the

number and percentage of patients who survived until discharge from hospital and number and percentage of patients who died whilst in hospital.

#### Number of critical care free days up to 30 days from randomisation

Number of critical care free days up to 30 days from randomisation will be analysed using a mixed-effects linear regression model, with a random intercept for country adjusting for planned surgical procedure category, age, gender, ASA grade, baseline haemoglobin, and baseline creatinine. ASA grade and procedure category will be included as categorical variables. Age, baseline haemoglobin, and baseline creatinine will be modelled using restricted cubic splines using the same approach as for the analysis of the primary outcome above (4, 5). Restricted maximum likelihood (REML) will be used.

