#### Number of critical care free days up to 30 days from randomisation

- If patient is alive 30 days from randomisation:
  - equal to 30 (total duration of level 2 critical stay within 30 days of randomisation + total duration of level 3 critical stay within 30 days of randomisation)
- If patient died within 30 days of randomisation
  - equal to (date of death date of randomisation) (total duration of level 2 critical stay within 30 days of randomisation + total duration of level 3 critical stay within 30 days of randomisation).
- Missing if:
  - o Total duration of level 2 critical stay within 30 days of randomisation is missing
  - o OR total duration of level 3 critical stay within 30 days of randomisation is missing
  - o Or Mortality at 30 days is missing

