# **Appendix 5: Tables**

Table 1 - Baseline table

|                                    | Complete data |            | Summary measure |            |  |
|------------------------------------|---------------|------------|-----------------|------------|--|
|                                    | Intervention  | Usual care | Intervention    | Usual care |  |
|                                    | no. (%)       | no. (%)    | (n=)            | (n=)       |  |
| Age – mean (SD)                    |               |            |                 |            |  |
| Female - no. (%)                   |               |            |                 |            |  |
| BMI (kg/m2) – mean (sd)            |               |            |                 |            |  |
| Planned surgical procedure – no.   |               |            |                 |            |  |
| (%)                                |               |            |                 |            |  |
| Resection of colon, rectum or      |               |            |                 |            |  |
| small bowel                        |               |            |                 |            |  |
| Resection of pancreas and          |               |            |                 |            |  |
| bowel                              |               |            |                 |            |  |
| Resection of stomach (non-         |               |            |                 |            |  |
| obesity surgery)                   |               |            |                 |            |  |
| Resection of oesophagus            |               |            |                 |            |  |
| (non-obesity surgery)              |               |            |                 |            |  |
| Obesity surgery                    |               |            |                 |            |  |
| Other major surgery involving      |               |            |                 |            |  |
| gut resection                      |               |            |                 |            |  |
| Planned level of care on the first |               |            |                 |            |  |
| night after surgical procedure –   |               |            |                 |            |  |
| no. (%)                            |               |            |                 |            |  |
| Critical care level 3              |               |            |                 |            |  |

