| Surgical technique – no. (%)     |               |              |                 |            |  |
| Open surgical technique          |               |              |                 |            |  |
| Laparoscopic or laparoscopic     |               |              |                 |            |  |
| assisted technique               |               |              |                 |            |  |
| Laparoscopic converted to        |               |              |                 |            |  |
| open                             |               |              |                 |            |  |
| Anaesthetic technique            |               |              |                 |            |  |
| General anaesthesia – no. (%)    |               |              |                 |            |  |
| Spinal / epidural – no. (%)      |               |              |                 |            |  |
| Tracheal tube removed at end     |               |              |                 |            |  |
| of surgery? – no. (%)            |               |              |                 |            |  |
| Time spent in post-anaesthesia   |               |              |                 |            |  |
| care unit at end of surgery –    |               |              |                 |            |  |
| median (IQR)                     |               |              |                 |            |  |
| Level of care on the first night |               |              |                 |            |  |
| after surgery – no. (%)          |               |              |                 |            |  |
| Critical care level 3            |               |              |                 |            |  |
| Critical care level 2            |               |              |                 |            |  |
| Post-anaesthesia care unit       |               |              |                 |            |  |
| Surgical ward                    |               |              |                 |            |  |
| Fluids – during surgery          |               |              |                 |            |  |
| Primary fluid used for volume    |               |              |                 |            |  |
| replacement during surgery –     |               |              |                 |            |  |
| no. (%)                          |               |              |                 |            |  |

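### The critical care free days model leaves out planned first-night level of care, a recorded baseline predictor, and so gives up a little precision

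*SAP*

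**What the plan says.** SAP Section 3 (Process Measures) defines a critical care free day as "a day in which the patient is alive and is not in a level 2 or level 3 critical care bed". Appendix 1 turns this into a count. For a patient alive at day 30 it is 30 minus the sum "total duration of level 2 critical stay within 30 days of randomisation + total duration of level 3 critical stay within 30 days of randomisation"; for a patient who died, the days from randomisation to death replace the 30. Neither place makes an exception for a stay that was planned before surgery.

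Section 5 analyses the count with a "mixed-effects linear regression model, with a random intercept for country", fitted by REML and "adjusting for planned surgical procedure category, age, gender, ASA grade, baseline haemoglobin, and baseline creatinine". The primary outcome model in the same section has the same covariates.

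Appendix 5 shows what else is recorded. Table 1, the baseline table, has a row beginning "Planned level of care on the first" night, with four categories: critical care level 3, critical care level 2, post-anaesthesia care unit and surgical ward. Table 2 has the corresponding row for what happened, "Level of care on the first night" after surgery. Table 13 has a row for critical care admission to treat a complication. All three are laid out by arm.

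**The concern.** The planned level of care bears on this outcome more directly than on any other in the SAP. A patient booked for level 2 or 3 on the first night who goes there has that time deducted, whatever the later course. The model nevertheless uses a covariate set chosen for postoperative infection. Elsewhere Section 5 does fit covariates to the outcome: the acute kidney injury and 24-hour cardiac event models are cut down, although there the reason is few events.

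The random intercept for country takes up differences in bed policy between countries. It does not take up differences between hospitals within a country, or between patients within a hospital. Procedure category and ASA grade may cover some of that, but planned level of care measures it directly.

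At stake is the precision of a formally tested comparison. Section 5 (General analysis principles) promises an effect estimate, a 95% confidence interval and a two-sided p-value for every process measure.

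**Working it through.** **Inputs from the SAP.** Section 4 gives 1251 patients per arm, 2502 in total. The SAP gives no mean, SD or expected difference for critical care free days.

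**Reproducing the plan's own figure.** For 30% against 25%, two-sided 5%, 80% power, pooled variance and no continuity correction:

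n per arm = [1.960 × √(2 × 0.275 × 0.725) + 0.842 × √(0.30 × 0.70 + 0.25 × 0.75)]² / 0.05² = 1251

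This matches the SAP. The power for 30% against 24% comes to 92.3%, against the stated 92%. Only the number per arm is carried forward.

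**Assumptions.** Half the patients are planned for level 2 or 3 (p = 0.5). The mean difference in critical care days between patients planned and not planned for critical care is d = 1.5 to 3 days. The SD of the outcome is 4 to 6 days. Planned level is reduced to two groups for the calculation.

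**Standard error without the covariate.** SE = SD × √(2/1251), which is 0.160 days for SD 4, 0.200 for SD 5 and 0.240 for SD 6.

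**Variance explained and its effect on the SE.** R² = p(1 − p)d²/SD². Adjustment multiplies the SE by √(1 − R²), so the unadjusted SE is larger than needed by 1/√(1 − R²) − 1.

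| d | SD | R² | √(1 − R²) | SE larger than needed by |
|---|---|---|---|---|
| 1.5 | 6 | 0.25 × 2.25/36 = 1.6% | 0.992 | 0.8% |
| 2 | 5 | 0.25 × 4/25 = 4.0% | 0.980 | 2.1% |
| 2 | 4 | 0.25 × 4/16 = 6.3% | 0.968 | 3.3% |
| 3 | 5 | 0.25 × 9/25 = 9.0% | 0.954 | 4.8% |
| 3 | 4 | 0.25 × 9/16 = 14.1% | 0.927 | 7.9% |

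The last row pairs the largest difference with the smallest SD and is the most favourable corner. In sample-size terms, R² of 1.6% to 9.0% corresponds to 2502 × [1/(1 − R²) − 1], or about 40 to 247 patients, for this measure only.

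**Check by simulation, on assumed inputs.** There were 2502 patients, with 30%, 50% or 70% planned for critical care. A planned patient had one routine night plus half a day more on average, and 15% of all patients had a recovery-related stay. With no difference between arms in placement, the mean estimated effect was within 0.003 days of zero with and without the covariate, so neither model is biased. The SE changed as follows:

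- 30% planned: 0.0942 to 0.0901, a fall of 4.3%
- 50% planned: 0.0960 to 0.0912, a fall of 5.0%
- 70% planned: 0.0961 to 0.0921, a fall of 4.2%

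The simulated models held no country, procedure or ASA terms. The R² formula likewise takes no account of them. Both therefore show the gain before any overlap with covariates already in the model.

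**The case against.** The strongest reply is that nothing here is an error. Sections 3 and 5 and Appendix 1 agree with one another, the estimate is unbiased as planned, and the marginal gain may be below 1% once country, procedure and ASA grade have taken their share. That the variable is a strong predictor follows from how the count is built; no figure in the SAP shows it. All of this stands. It limits the point to a small improvement in precision, but a small improvement at almost no cost is still worth taking.

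A reader might infer something stronger. The trial is open, and the algorithm covers "infusion during and for four hours following surgery". Staff might therefore place intervention patients in a level 2 or 3 bed to deliver it, and that night would count against the intervention. The SAP does not support this as a finding of bias, for four reasons:

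- It nowhere says that the infusion needs a level 2 or 3 bed. Tables 1 and 2 list the post-anaesthesia care unit separately, and the definition does not count it as critical care. Table 2 does record extra research staff in the four hours after surgery, but that concerns staff, not beds.
- The SAP calls this a process measure, not a measure of recovery. Extra bed use caused by allocation would be a real effect on it.
- Such an effect would not be hidden. Tables 1, 2 and 13 report planned level, actual first-night level and complication-driven admission by arm, though for description only.
- The covariate would not address it. In the simulation, one night in critical care for 10 to 20% of the intervention patients not planned for it moved the estimate by 0.03 to 0.14 days against the intervention, equally with and without adjustment.

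Nor should the first night be removed according to where the patient actually went. That is a post-randomisation variable, and removing it would also erase unplanned first-night admissions, including those for intraoperative complications.

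**Conclusion.** The point holds as a matter of precision only. The model omits a recorded baseline variable that directly predicts the days deducted. The arm comparison remains unbiased. Its SE is about 1 to 5% larger than it need be, for R² of about 2 to 9%; the extreme corner of the assumed range gives about 8%. These sizes rest entirely on the assumed share planned for critical care, mean difference and SD, and overlap with country, procedure and ASA grade would reduce them. The point is minor: it concerns one process measure, and the primary, secondary and safety analyses and the sample size are unaffected.

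**What to change.** In SAP Section 5, under the critical care free days analysis, add planned level of care on the first night as a categorical covariate with the four Table 1 categories. Make the same change in the matching Appendix 3 code; that code is not visible in the copy at hand, so the covariate list above is taken from Section 5. Use the value recorded before allocation, and confirm this from the case report form, because in an open trial a plan entered afterwards could reflect the allocation. State how the SAP's mean imputation applies to a categorical covariate if any values are missing.

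Report the result beside Tables 1, 2 and 13, so that planned placement, actual placement and complication-driven admission can be read together. No further analysis is needed.

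The cost is three more terms in a linear model on 2502 patients, using data already collected. The change should be dated in the revision history and made before outcomes are seen by arm.
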